**Schema**

Cycle = 28 days  
Accrual Goal: 35

## 1. Introduction

### 1.1 Ipatasertib

[figure not shown]
Ipatasertib (GDC-0068) is a selective, ATP-competitive inhibitor of AKT. *In vitro*, Ipatasertib inhibits all 3 isoforms of AKT (IC50 of AKT1, AKT2 and AKT3 of 5, 18 and 8nM respectively). Screening against a broad panel of 225 kinases determined that Ipatasertib is highly selective, acting as a potent inhibitor against only three additional kinases (including > 70% inhibition against p70S6K – IC50 is 860 nM). Thus, Ipatasertib displays a > 100-fold selectivity for AKT1 over the next most potentially inhibited non-AKT kinase, i.e. p70S6K. In PC-3 (PTEN mutant, prostate), BT474M1 (PIK3CA mutant, HER2+ breast), and IGROV-1 (PTEN and PIK3CA mutant, ovarian) cell lines, downstream targets of AKT including PRAS40, Fox01, Fox03, 4EBP1, and S6 are inhibited in a dose- and time-dependent manner. In PC-3, BT474M1 and MCF7-neo/HER2 (PIK3CA mutant, HER2+ breast) cells, a dose-dependent increase in G0-G1 phase population has been identified, as well as an increase in apoptotic and necrotic populations in the breast cell lines, as determined by Annexin V/PI staining. Sensitivity to Ipatasertib is strongly associated with pAKT levels above the median value, as well as with loss of PTEN/PTEN mutation. Cell lines with a PIK3CA kinase mutation (i.e. exon 20) also demonstrate increased sensitivity, while those with a helical (i.e. exon 9) or other domain mutation do not. Genentech/Roche has internal data that confirm the growth factor-independent activation of AKT by AKT1 mutations E17K, L52R, D323H, D323Y, Q79K, W80R, AKT2 mutation E17K, and AKT3 mutation E17K. All of these mutations sensitize cells to Ipatasertib in an IL-3-independent BaF3 cell assay. In addition, Ipatasertib demonstrated robust tumor growth inhibition in xenograft models of human cancer cell lines with alterations known to lead to AKT activation, such as LNCaP (PTEN-null, prostate), PC3 (PTEN-null, prostate), HGC-27 (PTEN-null, gastric), HCC1954 (PIK3CA mutant, HER2+ breast), TOV-21G (PTEN-null & PIK3CA mutant, ovarian), and 537MEL (PTEN-null, melanoma), as well as PDX models with PTEN loss or PIK3CA mutations.

There are currently no FDA approved AKT inhibitors for cancer treatment. Ipatasertib is currently under investigation in phase I, II, and III clinical trials in castration resistant prostate cancer and metastatic breast cancer ([www.clinicaltrials.gov](http://www.clinicaltrials.gov)). In a three-stage study, 30 patients were enrolled in the dose-escalation (stage I) and 22 patients in the two dose expansion cohorts (11 metastatic breast cancer and 5 patients with metastatic castration-resistant prostate cancer; stage II), or all solid tumors (n=6, stage III). The most common cancers were breast cancer (n=16) or colorectal cancer (n=14), with a median of 6 prior lines of therapy (range, 1-17). Oral Ipatasertib was administered daily for 21 days followed by 7 days off (21/7 day dosing schedule) every 28 days with doses ranging from 25-800 mg. Dose limiting toxicities (DLTs) at 800 mg were asthenia and nausea. The maximum tolerated dose for Ipatasertib was 600 mg daily on a 21-day on/7-day off schedule which was used for the expansion cohorts in stage II and stage III; however, the recommended dose for further development is 400 mg daily based upon overall tolerability profile. This dose level is being evaluated in continuous daily dosing, as well as 21-day on/7-day off schedule in phase III studies, with the schedule depending on the combination therapy studied.

In 51 treated patients in the single agent study, the most common causally-related grade 2 or greater adverse events across all dose levels were as follows: diarrhea (35%), nausea (27%), asthenia (25%), hyperglycemia (10%), decreased appetite 6%, rash (6%), and vomiting (6%). Grade 3 events were diarrhea (n=4), asthenia (n=3), hypercholesterolemia (n=1), hyperglycemia (n=1), hypophosphatemia (n=1), nausea (n=1), and toxic skin eruption (n=1). No grade 4 events were observed. Timing to the first onset of diarrhea, nausea, fatigue, and rash typically occurred during cycle 1. As proof of mechanism, reduction in the substrates pGSK3 $\beta$  and pPRAS40 was demonstrated in platelet-rich plasma. In terms of exposure, Ipatasertib  $\geq$  400 mg was associated with pGSK3 $\beta$  reduction  $\geq$  80%, and even at doses  $<$  100 mg greater than 50% inhibition was observed. In addition, comparing pretreatment and on-treatment tumor biopsies, there was a reduction in pRAS40, pEBP1, pS6, and pmTOR in a dose-dependent manner, as measured by reverse phase protein array.

## 1.2 Supporting Preliminary Data

[figure not shown]
The PI3K-AKT pathway is one of the most commonly altered pathways in cancer, including mutations, somatic copy number abnormalities, increased expression, and aberrant signaling. A number of intrinsic and extrinsic survival signals induced by several receptors are thought to be transduced downstream through the PI3K/AKT pathway. In addition, hyperactivity of this pathway promotes resistance to pro-apoptotic signaling induced by chemotherapy and other anti-neoplastic therapies.

### Overview of PI3K-AKT pathway:

The PI3K-AKT pathway can be activated upstream by a wide variety of receptor protein tyrosine kinases (RTKs; in particular growth factor receptors), cytokine receptors, intracellular tyrosine kinases, G-protein coupled receptors, and intracellular small GTPases such as Ras. In the case of RTKs, activation by ligand binding results in the non-covalent association of phosphatidylinositol-3 kinases (PI3Ks) with phosphotyrosine consensus motifs on the intracellular domain of the RTK. One or two src-homology 2 (SH2) domains on the beta

(regulatory) subunit of PI3K participate in this interaction, which results in allosteric changes to the catalytic alpha subunit of PI3K, leading to functional activation. The phosphatidylinositol 3,4,5-trisphosphate (PIP3) is generated as a result of phosphorylation by activated PI3K, and resides on the inner side of the plasma membrane. PIP3 is then able to activate a number of proteins, including PDK1, AKT, and other serine/threonine kinases. The pleckstrin homology domain of AKT interacts with PIP3, resulting in transient localization of AKT to the inner membrane and subsequent phosphorylation of the Thr308 and Ser473 residues by phosphoinositide-dependent kinases 1 and 2 (PDK1, PDK2), respectively. PDK1 itself is activated by PIP3, while PDK2 has been recently identified as mTORC2 (the complex rictor/mTOR). Phosphorylated AKT (p-AKT) represents the active form. The tumor suppressor phosphatase and tensin homologue deleted on chromosome 10 (PTEN) is an important negative regulator of the PI3K/AKT pathway, as it functions to rapidly convert PIP3 back to PIP2.

Activation of AKT regulates multiple cellular processes including cell survival, cell proliferation, cell growth, and various aspects of cellular metabolism. AKT (Protein Kinase B) is an evolutionarily conserved serine threonine kinase with 3 forms in mammalian species, AKT1, AKT2, and AKT3, all encoded by different genes. AKT represents an important signaling hub with well over 100 downstream target proteins that it is able to activate or inactivate through phosphorylation of serine and threonine residues. AKT modulates cell survival, cell cycle progression, and cellular growth through phosphorylation of these downstream targets, including inhibition of Bad and caspase 9, phosphorylation of Mdm2 leading to p53 ubiquitination, and phosphorylation of mTOR, respectively. Although the subset of downstream AKT effectors that are most crucial for tumor development have not been entirely elucidated, there is substantial evidence that mammalian target of rapamycin complex 1 (mTORC1) plays an important role. AKT activates mTORC1 by several mechanisms including phosphorylation and inhibition of the tumor suppressor tuberous sclerosis complex 2 (TSC2) that binds to and negatively regulates mTORC1 activity (Fig 2).

**Fig 2:** The PI3K/AKT pathway. The role of AKT and downstream effectors are demonstrated.

#### Alterations to the PI3K-AKT pathway in cancer:

Mutations in genes encoding for the subunits of PI3K represent some of the most commonly mutated genes in all of cancer, with kinase domain activating point mutations in the PIK3CA gene (which encodes for p110 $\alpha$ ), second only to p53 as the most commonly occurring mutations in all tumor specimens in The Cancer

Genome Atlas (TCGA). PTEN loss of function mutations, silencing by methylation and other epigenetic changes, and large scale chromosomal changes leading to loss of PTEN are also amongst the more common aberrations seen across many different cancer types, and in particular in metastatic cancer. Germline mutations in PTEN are responsible for the Cowden familial cancer syndrome. Mutations in PTEN and PIK3CA do not appear to be mutually exclusive, underscoring the complex functioning of the various components of the PI3K-AKT pathway.

On the other hand, mutations in AKT genes are rarely found in human cancers to date. Activating mutations have been described in a small percentage of breast cancers, head and neck squamous cell carcinomas, endometrial cancer, non-small cell lung cancer, and renal cancers. An AKT1 point mutation in the pleckstrin homology domain that replaces a glutamic acid with lysine (E17K) at residue 17 is the most commonly reported mutation, and is thought to confer increased activity by promoting its localization to the plasma membrane. AKT E17K mutation, for example, is seen in 2-3% of breast cancer, and other AKT mutations have been seen in this tumor as well (BROAD, SANGER, TCGA). AKT1 mutations were seen in luminal A, B and the HER2 subset, but not in basal type. Other activating mutations reported in the literature include the E49K (AKT1) and G171R substitutions (AKT3), which occur in the pleckstrin homology domain and in the kinase domain, respectively. Measurement of p-AKT levels in both tumors and cancer cell lines confirms a quantitative increase in activated AKT as a consequence of these point mutations, and overall levels of p-AKT appear to correlate with sensitivity to AKT inhibition.

In addition to mutations, there are other means of augmenting AKT activity, including AKT gene amplification and AKT rearrangements. However, there is no evidence of pre-clinical or clinical benefit of an AKT inhibitor, such as Ipatasertib, with AKT amplifications or fusions. To date there is no approved targeted treatment for patients with AKT mutations; this trial may produce clinical validation data that such patients can respond to an AKT inhibitor.

Rev. Add25

### 1.3 Exclusion of Breast Cancer

Due to recent findings that an excess of breast cancer patients (n=18/26) have been accrued to the trial it is now necessary to limit their accrual to avoid overrepresentation of tumors of a particular subtype that would make the 'tumor agnostic' intent of the subprotocol unachievable. This has been modified under 'eligibility criteria.'

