## 2. Selection of Patients

Each of the criteria in the checklist that follows must be met, along with the eligibility in the MATCH Master Protocol, in order for a patient to be considered eligible for this study. Use the checklist to confirm a patient's eligibility. For each patient, this checklist must be photocopied, completed and maintained in the patient's chart.

**In calculating days of tests and measurements, the day a test or measurement is done is considered Day 0. Therefore, if a test is done on a Monday, the Monday four weeks later would be considered Day 28.**

ECOG-ACRIN Patient No. \_\_\_\_\_

Patient's Initials (L, F, M) \_\_\_\_\_

Physician Signature and Date \_\_\_\_\_

**NOTE:** Policy does not allow for the issuance of waivers to any protocol specified criteria ([http://ctep.cancer.gov/protocolDevelopment/policies\\_deviations.htm](http://ctep.cancer.gov/protocolDevelopment/policies_deviations.htm)). Therefore, all eligibility criteria listed in Section 2 must be met, without exception. The registration of individuals who do not meet all criteria listed in Section 2 can result in the participant being censored from the analysis of the study, and the citation of a major protocol violation during an audit. All questions regarding clarification of eligibility criteria must be directed to the Group's Executive Officer ([[contact]](mailto:[contact])) or the Group's Regulatory Officer ([[contact]](mailto:[contact])).

**NOTE:** Institutions may use the eligibility checklist as source documentation if it has been reviewed, signed, and dated prior to registration/randomization by the treating physician.

**NOTE:** All patients must have signed the relevant treatment consent form

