### 2.1 Eligibility Criteria

- \_\_\_\_\_ 2.1.1 Patients must fulfill all eligibility criteria outlined in Section 3.1 of MATCH Master Protocol (excluding Section 3.1.6) at the time of registration to treatment step (Step 1, 3, 5, 7).
- \_\_\_\_\_ 2.1.2 Patients must have an AKT mutation as determined via the MATCH Master Protocol and described in [Appendix II](#). See [Appendix II](#) for information on the AKT mutation and corresponding Levels of Evidence.
- \_\_\_\_\_ 2.1.3 Patients with breast cancer are excluded.
- \_\_\_\_\_ 2.1.4 Patients with castration-resistant prostate cancer should maintain castrate levels of testosterone (i.e., with GnRH agonists or through surgical castration). Patients are allowed to continue abiraterone acetate / prednisone with Ipatasertib if the patient just progressed on abiraterone acetate / prednisone.
- \_\_\_\_\_ 2.1.5 Patients must not have known hypersensitivity to Ipatasertib or compounds of similar chemical or biologic composition.
- \_\_\_\_\_ 2.1.6 Patients with known KRAS, NRAS, HRAS, or BRAF mutations are not eligible for this protocol, as these mutations may lead to limited response due to resistance.

Rev. Add25

\_\_\_\_\_ 2.1.7 Patients with diabetes or risk for hyperglycemia are eligible. Patients with diabetes mellitus should be on a stable dose of oral hypoglycemic agents for  $\geq$  4 weeks and appropriate diet. Patients with diabetes mellitus may enter the study unless any of the following exclusion criteria are fulfilled:

- Baseline fasting glucose value of  $>8.9$  mmol/L or 160 mg/dL (fasting is defined as no calorific intake for at least 8 hours)
- Patients not on a stable dose of oral hypoglycemic medication for  $\geq$  4 weeks and appropriate diet
- Insulin required for routine diabetic management and control
- More than two oral hypoglycemic medications required for routine diabetic management and control
- Hemoglobin A1C  $\geq 7.5\%$

\_\_\_\_\_ 2.1.8 Prior PI3K and mTOR inhibitors are allowed, including in the metastatic setting. Prior AKT inhibitors are excluded (See [Appendix IV](#)).

\_\_\_\_\_ 2.1.9 Patients with a history of inflammatory bowel diseases (Crohn's disease and ulcerative colitis) or active diverticulitis are not eligible.

\_\_\_\_\_ 2.1.10 Patients may not have received strong inhibitors or potent inducers or substrates of CYP3A4/5 within 2 weeks before the first dose of study treatment (3 weeks for St John's Wort). See Section [5.1.8](#) and [Appendix III](#).

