#### Hormone Therapy (Breast Cancer and/or Prostate Cancer)

If the patient has HR positive/HER2 negative unresectable breast cancer, (s)he is allowed to continue fulvestrant or an aromatase inhibitor (anastrazole, letrozole, exemestane) with Ipatasertib if (s)he most recently progressed on this anti-estrogen therapy. For instance, if the last treatment was fulvestrant, the patient is allowed to continue the fulvestrant in combination with Ipatasertib. If the patient previously was receiving GnRH agonist (such as leuprolide or goserelin), this should continue as previously administered.

SERMs, such as tamoxifen or toremifene, are not allowed.

If the patient has metastatic castration resistant prostate cancer, he is allowed to continue abiraterone if he just progressed on this agent. GnRH agonists (such as leuprolide or goserelin) are allowed. Prednisone/prednisolone is allowed along with this combination – up to 10 mg po daily (5 mg po bid is allowed).

The patient should continue on the same dose and schedule of the prior hormone therapy as was previously taken. Hormone therapy administration is per FDA-approved package labeling.

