3. At end of all MATCH study treatments, blood specimens and/or research biopsy after consent and registration to Step 8

Please refer to Section 4 of the MATCH Master Protocol to determine whether the patient proceeds to the next screening step or to follow-up (with a potential end of treatment biopsy for research purposes on Step 8). Samples are to be submitted as outlined in Section 9 of the MATCH Master Protocol. To order Step 2/4 Screening or Step 8 kits, complete the EAY131 Collection and Shipping Kit Order Form (See Appendix XII of the MATCH Master Protocol) and fax to [contact].

4. For Cycle 1, if the following tests/assessments occurred within 7 days of Day 1, they do not need to be repeated at this time point: H&P, Weight, Vital Signs; Performance Status; CBC w/diff, platelets; Serum chemistry; Concomitant Medications.

5. The patient will also return for Day 15 (+/- 5 days) for pre-dose on cycle 1 and cycle 2. Fasting basic metabolic panel (including glucose), and CBC w/diff will be collected. Hyperglycemia management is described in Section [3.4](#).

If the patient has Hormone Receptor positive, HER2 negative unresectable breast cancer, the patient is allowed to continue the fulvestrant or aromatase inhibitor that (s)he just progressed on. For the aromatase inhibitor, patients are NOT allowed to switch within class (for instance, letrozole to anastrazole). GnRH agonists are allowed to continue as previously administered. Dosing should be followed, as per the FDA-approved package labeling. SERMS, such as tamoxifen or toremifene, are not allowed. This study is no longer accruing patients with metastatic breast cancer.

7. If the patient has castration resistant prostate cancer, he is allowed to continue the abiraterone that he just progressed on. For guidance, it is recommended to follow the prescribing information for abiraterone.
8. If the patient is given Fulvestrant and/or a GnRH agonist, these should be given on D1 of the cycle (+/- 7 days).
9. All patients should receive loperamide (2 mg oral twice a day or 4 mg once a day) as prophylaxis for diarrhea in the first cycle if allowed by local guidance. Investigators are encouraged to continue this dosing for the remainder of the study, and the prophylaxis dose may be adjusted as necessary, using their discretion based on clinical judgment and per local guidance.

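### Does closing breast accrual at 18 of 26, with the goal still 35, leave the tumor-agnostic aim unprotected?

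*Protocol*

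**What the plan says.** Section 1.3 (Exclusion of Breast Cancer) states that "an excess of breast cancer patients (n=18/26) have been accrued to the trial" and that their accrual now has to be limited, in order to "avoid overrepresentation of tumors of a particular subtype that would make the 'tumor agnostic' intent of the subprotocol unachievable". For the remedy it refers the reader to the eligibility criteria: "This has been modified under 'eligibility criteria".

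Two places carry this out. Criterion 2.1.3 reads "Patients with breast cancer are excluded", and a footnote to the table in Section 4.1 adds "This study is no longer accruing patients with metastatic breast cancer". The Schema gives "Accrual Goal: 35".

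Two other passages bear on the point. Section 2 warns that registering someone who does not meet every criterion "can result in the participant being censored from the analysis of the study", so the analysed group may be smaller than the enrolled group. The hormone therapy text under Section 3.1 says that a patient with HR-positive/HER2-negative unresectable breast cancer "is allowed to continue fulvestrant or an aromatase inhibitor" if that was the treatment on which the disease last progressed.

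The subprotocol has no statistics section. It gives no response threshold, error rate, power or decision rule for the goal of 35. It refers to the MATCH Master Protocol for core eligibility, adverse event reporting, follow-up, the base study parameters and translational work.

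**The concern.** Section 1.3 itself says that too many patients with one tumor type would defeat the purpose of the subprotocol. Its remedy acts only on future patients. The 18 breast patients already enrolled stay in the cohort, the goal has not moved, and there are too few places left for other tumors to outnumber them. At first sight the amendment names a problem and then stops short of solving it.

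The possible harm is in interpretation. If the result is read as one overall response rate, activity confined to breast cancer could pass for activity across tumor types. Some breast patients may also be continuing an anti-estrogen, so a response in that group may not be due to ipatasertib alone. Section 1.3 neither says how the two groups will be weighed nor points to a place that does.

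**Working it through.** **Inputs.** From Section 1.3: 18 breast patients among 26 accrued. From the Schema: goal 35. From criterion 2.1.3: no further breast patients.

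**Cohort mix**

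- Now: 18/26 = 69.2% breast; 26 − 18 = 8 non-breast.
- Places left: 35 − 26 = 9.
- At the goal with the exclusion: 18/35 = 51.4% breast; 8 + 9 = 17 non-breast.
- At the goal had accrual continued in the same proportion: 18 + 9 × 18/26 = 24.2, so about 24 breast and 11 non-breast.
- Stopping early raises the breast share: 18/30 = 60.0%, 18/34 = 52.9%.
- Parity would need 36 patients (18/36 = 50.0%), and a non-breast majority 37 (18/37 = 48.6%).

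**How firm the majority is.** These shares are of enrolled patients. If one breast patient leaves the analysis the share is 17/34 = 50.0%; if two leave, 16/33 = 48.5%. If two non-breast patients leave, it is 18/33 = 54.5%. Whether breast is a majority of those analysed can turn on one or two patients.

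**What the exclusion gains.** Exact (Clopper-Pearson) 95% upper limits when no non-breast patient responds:

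| Non-breast patients | Situation | Upper limit for 0 responses |
|---|---|---|
| 8 | at the time of the change | 36.9% |
| 11 | at 35, no exclusion | 28.5% |
| 17 | at 35, with exclusion | 19.5% |

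**What a pooled rate can hide.** An overall 5/35 is 14.3% (95% CI 4.8% to 30.3%). It could be 5/18 breast with 0/17 non-breast, where the non-breast rate is 0% with an upper limit of 19.5%. It could equally be 2/18 with 3/17, where the non-breast rate is 17.6% (3.8% to 43.4%). The overall figure cannot separate these.

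**How likely a misleading result is.** This needs response rates and a decision rule, and the protocol gives neither, so everything here is assumed. Take no activity outside breast and a breast response rate of 30%. The chance of reaching r responses in 35 is then P(Bin(18, 0.3) ≥ r), or P(Bin(24, 0.3) ≥ r) without the exclusion:

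| Assumed rule | 18 breast / 17 non-breast | 24 breast / 11 non-breast |
|---|---|---|
| at least 5 of 35 | 66.7% | 88.9% |
| at least 6 of 35 | 46.6% | 77.1% |
| at least 8 of 35 | 14.1% | 43.5% |

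With the breast rate varied from 20% to 40% over the same three rules, the 18/17 split gives 1.6% to 91%. A range that wide does not establish the size of any problem. What the table does show is that, for every assumed rule, the amended mix is less exposed than the mix it replaced.

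**The case for a change.** The strongest argument for a change is that the breast excess is peculiar to this subprotocol. A general rule in the Master Protocol may not have foreseen it, and Section 1.3 is where the problem is declared and treated as dealt with. Other sections refer explicitly to the Master Protocol; this one does not. Stating now how the 18 patients count would cost two or three sentences and one table row, and would guard against a split chosen after the results are known. Nor does this argument need the 50% line: a cohort that is nearly half one histology makes a pooled rate just as ambiguous.

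Part of this stands. The arithmetic is right, and the missing cross-reference is real. It would do no harm for Section 1.3 to cite where analysis by tumor type is defined, or for response to be listed by histology beside the overall rate.

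The rest does not carry. Once the 50% line is given up, what remains is a general caution about pooling: the same ambiguity would exist with 18 of 37 breast patients, or with 10 of 35. A separate non-breast estimate would not settle the tumor-agnostic question either. At most 17 patients would be spread over tumor types that the protocol does not list, and three responses among them could all come from one histology. A simple listing of responses by tumor type would tell the reader at least as much, and analysts of a basket cohort can produce it without an instruction in Section 1.3.

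**Conclusion.** No change to the plan follows. At a total of 35, breast will make up at least 18/35 (51.4%) of enrolled patients, down from 69.2%, with at most 17 non-breast patients instead of about 11. That is a fair trade-off: it keeps the goal, uses every remaining place for other tumors, and tightens what can be learned about them (upper limit for zero responses 19.5% instead of 28.5%).

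Nothing in the protocol is misstated or contradicted. Section 1.3 says breast accrual must be limited, and criterion 2.1.3 and the Section 4.1 footnote limit it. A majority as the mark of overrepresentation is a line the protocol does not draw, and the excess over that line is one patient.

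Section 1.3's silence on the analysis fits a subprotocol that contains no statistical section at all; reporting by tumor type is commonly left to the Master Protocol or SAP. The conclusion assumes that enrolment stops at 35 and that no further breast patients entered after the 18 reported; one more would give 19/35 = 54.3%. It does not assume that a rule for tumor type exists elsewhere, since neither of those documents was available to check.
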